- Start the study only after all legal requirements in my country have been fulfilled.
- Obtain informed consent for all subjects prior to performing any study-related action.
- Permit study-related monitoring, audits, IEC/IRB review, and regulatory inspections and provide direct access to all study-related records, source documents, subject files, and case report forms for the sponsor, monitor, auditor, IEC/IRB, or regulatory authority upon request.
- Use all study materials only as specified in the clinical study protocol.
- Report to the responsible product safety officer, within 24 hours, any serious adverse event (SAE), and serious adverse device effect (SADE), whether considered related or not related to the investigational device.
- Provide to the sponsor, prior to initiating the study, my curriculum vitae, including details of relevant experience and an explanation of any prior terminated research (if applicable).
- Provide written disclosure of any financial interest, in accordance with 21 CFR Part 54, and promptly update this information if changes occur during or within one year after study completion.

Furthermore, I understand that:

- Changes to this protocol must be made in the form of an amendment that has the prior written approval of Merz and any applicable IEC/IRB or regulatory authority.
- The content of the clinical study protocol is confidential and proprietary to Merz.
- Any deviation from the clinical study protocol may lead to early termination of the study site.

Principal Investigator (print name)

Date (dd-MMM-year)

Signature

PROTOCOL SYNOPSIS

Protocol Title	Evaluation of Effectiveness and Safety of Radiesse (+) to Improve the Contour of Jawline by Adding Volume to the Jawline
Protocol Number	M900391004
Active Product	Radiesse (+)
Study Phase	Device Pre-Market - Pivotal study
Indication	Deep (subdermal and/or supraperiosteal) injection to improve the contour of jawline by adding volume to the jawline.
Number of Sites and Countries	This study will be conducted in the United States at up to 15 sites.
Number of Study Subjects	Approximately 180 subjects will be enrolled, with approximately 120 subjects in the treatment group and 60 subjects in the control/delayed-treatment group.
Objective(s)	
Effectiveness
 
To demonstrate the effectiveness of Radiesse (+) following deep (subdermal and/or supraperiosteal) injection to improve the contour of jawline by adding volume to the jawline. 
Safety
 
Identification and description of adverse events (AEs) and serious adverse events (SAEs) during the course of the study.
Key Endpoints	
Primary
 
Comparison of the responder rate between the treatment group and the untreated control group at Week 12, according to the Merz Jawline Assessment Scale (MJAS). Treatment response is defined as \geq 1-point improvement 
Secondary
 
FACE-Q satisfaction with lower face and jawline among treated subjects as average percent change from baseline to Week 12.Global Aesthetic Improvement Scale (GAIS) scores for treated subjects at Week 12, as completed by the treating investigator.GAIS scores for treated subjects at Week 12, as completed by the subject.

	
responder rates in the treatment group and the untreated control group at Week 12, according to the MJAS
 
Treatment
 
response is defined as ≥ 1-point improvement compared to baseline.
 
Safety
 
 device- and/or injection-related AEs and SAEs observed during the study.

Study Design Overview
	
This is a 60-week, prospective, multicenter, randomized, controlled, pivotal clinical study to investigate the effectiveness and safety of Radiesse (+) to improve the contour of jawline by adding volume to the jawline. Approximately, 180 subjects with a grade of 2 or 3 on the MJAS will be enrolled into the study.
 
Enrolled subjects will be randomized (2:1 allocation ratio) to either receive treatment with Radiesse (+) or delayed treatment (i.e., untreated controls until primary endpoint assessment at Week 12 after which the controls are eligible for treatment and then followed for the remainder of the study).
 
Subjects who do not achieve a ≥ 1-point improvement on the MJAS will be required to have a touch-up injection

	
[REDACTED]
 
[REDACTED] The primary effectiveness endpoint will be assessed 12 weeks post-treatment. Subjects randomized to the treatment group at baseline will have the option of a retreatment with Radiesse (+), upon agreement between the subject and the investigator, at Week 48 and will then be followed for an additional 12 weeks, for a total study duration of 60 weeks. Subjects who do not receive a retreatment at Week 48 will also be followed until Week 60.
 
Subjects randomized to the control group at baseline will remain untreated until completion of the primary endpoint assessment at Week 12. After all primary endpoint assessments have been completed, these control subjects will be treated with Radiesse (+) (i.e., delayed treatment) and will then be followed for 48 weeks post-treatment. Subjects [REDACTED]
 
[REDACTED] may have a touch-up injection in one or both jawline(s) for further correction at the discretion of the treating investigator and the subject. Control subjects will not be offered retreatment.
 
[REDACTED]

	
To be eligible for the study, each subject must meet all of the following main inclusion criteria:
 
 Has right and left jawline ratings of 2 or 3 (moderate or severe) on the MJA Has the same MJAS rating on both jawlines (i.e., jawlines are symmetrical). Is ≥ 22 and ≤ 65 years of age.
Key Inclusion/ Exclusion Criteria	
[REDACTED]
 
Subjects meeting any of the following main exclusion criteria are not eligible to participate in the study:
 
[REDACTED]

- [REDACTED] Ever been treated with fat injections or permanent fillers (e.g., silicone, polymethylmethacrylate (PMMA)) in the lower face and/or jawline area or plans to receive such treatments during participation in the study.
- [REDACTED] Been treated with semi-permanent dermal fillers (e.g., poly L-lactic acid) in the lower face and/or jawline area in the past 5 years or plans to receive such treatments during participation in the study.

[REDACTED]

[figure not shown]
Table of Contents

1	Introduction.....	15
1.1	Background and rationale	15
1.2	Potential benefits and risks	16
2	Study objectives and endpoints	19
2.1	Objectives	19
2.1.1	Effectiveness	19
2.1.2	Safety	19
2.2	Endpoints	19
2.2.1	Primary endpoint.....	19
2.2.2	Secondary endpoints	19
2.2.3		
2.2.4	Safety endpoints.....	23

SAP	Statistical analysis plan
SOC	System organ class

Abbreviation/Term	Definition
Tx	Treatment
UADE	Unanticipated adverse device effects
UV	Ultraviolet
Wk	Week

[figure not shown]
1 INTRODUCTION

1.1 Background and rationale

As part of the natural aging process, multiple factors lead to a decreased level of volume or noticeable contour of the jawline, including loss of bony structures, atrophy (volume loss) and descent of fat [1]. Volume loss in relation to the attachment points of the skin to the underlying superficial muscular aponeurotic system and/ or bone results in specific patterns of deflation, pseudoptosis, and shadowing – all of which characterize the aging face. As soft tissue fullness shifts from the upper face to the lower face, the aging face loses its youthful heart-shaped appearance and takes on a heavy, rectangular shape [2]. A surgical facelift is the standard treatment used to address these signs of aging and aid in redefining the jawline. However, it is, by definition, an invasive procedure and thus deemed less safe than other non-invasive alternatives, including radiofrequency/ ultrasonic skin tightening or the use of dermal fillers. As the demographics of aesthetic patients evolve, patients are seeking increasingly less invasive procedures with visible results and reduced downtime [3].

Dermal fillers have been identified as a treatment option to straighten and reestablish volume and contour of the jawline; fillers also provide an opportunity to enhance the size of the jaw by adding volume in the front at the chin and/or on the sides of the jaw. This enhancement can be achieved through filling volume and contour deficits, resulting in the enhancement of ptotic superficial compartments, repositioning of superficial fat, and/or tightening the skin around the jawline [3][4]. In order to reestablish or correct the mandibular angle and to achieve a satisfactory filling effect, a dermal filler with high elasticity and viscosity provides the best volumizing capacity [2].

Over a decade of clinical experience, multiple published reports have documented the use of dermal fillers, including Radiesse, to improve the jawline [4][5][6][7][8][9][10][11]. The available literature supports both the effectiveness and safety of Radiesse when used in the jawline, from the mentum through the mandibular angle. Multiple authors report favorable results at 6 and 12 months following placement of the product, noting both physician and patient satisfaction. A low number of procedure-related adverse events, such as pain, erythema, edema, and bruising, were reported – most of which were mild and resolved quickly without intervention. Overall, the safety profile of jawline treatment is favorable and comparable to other established treatment indications.

The published literature on the effectiveness and safety of Radiesse used in the jawline justifies the need for Merz North America, Inc. to conduct a large, robust randomized clinical trial among subjects who desire improvement of jawline volume and contour using Radiesse (+).

1.2 Potential benefits and risks

The potential benefit of Radiesse (+) when used in the jawline is to improve contour by adding volume to the jawline.

In a European observational study using calcium hydroxylapatite (CaHA) for the treatment of the jawline in a routine setting, the findings showed improvements in jawline contour compared with baseline, and these findings were statistically significant at each visit, with scores of 2.42 (moderate to severe sagging) at baseline, 1.02 (mild) at Day 30 ($p<0.0001$), 1.11 at Day 180 ($p<0.0001$), and 1.45 at Day 360 ($p<0.0015$). Overall, CaHA was found to be very effective for restoring jawline contour in clinical practice with high levels of physician and subject satisfaction [12].

[figure not shown]
The potential risks associated with the use of Radiesse (+) for deep (subdermal and/or supraperiosteal) injection into the jawline are similar to other lidocaine-containing, commercially available, cosmetic dermal fillers. No new risks have been identified for use of Radiesse (+) in the jawline, including product placement in deep (subdermal and/or supraperiosteal) injection planes.

[figure not shown]
Potential treatment-site responses associated with Radiesse (+) consist mainly of ecchymosis, edema, erythema, pain, pruritus, discoloration, tenderness, mild infection, and the potential for nodule development. In previous studies, common injection-procedure reactions have generally resolved within seven days of treatment. Less common but possible side effects also include the following: migration, over-correction, reactivation of herpes, impact to jaw function, persistent swelling, persistent nodules, and/or serious infection.

An additional harm or risk, which is not an adverse event, includes disappointment due to lack of or reduced performance and/or undesirable aesthetic effect.

Rare but serious adverse events associated with the intravascular injection of soft-tissue fillers in the face have been reported and include: temporary or permanent vision impairment; blindness; cerebral ischemia or cerebral hemorrhage, leading to stroke; skin necrosis; abscesses; granulomas; and damage to the underlying facial structures. Unintentional implantation of Radiesse (+) into the vasculature may lead to embolization, occlusion of the vessels, ischemia, or infarction.

Lidocaine is commercially available and frequently used as a local and regional anesthetic agent. The potential benefit of lidocaine is the reduction of injection-related pain and discomfort. Potential side effects associated with lidocaine are a risk of participating in this study and include: lightheadedness; nervousness; apprehension; euphoria; confusion; dizziness; drowsiness; ringing noise in the ears; blurred or double vision; vomiting; sensations of heat, cold or numbness; twitching; tremors; convulsions; unconsciousness; respiratory depression and arrest; slow heartbeat; hypotension; and/or cardiovascular collapse, which may lead to cardiac arrest. However, these side effects are unlikely to occur at the low doses of lidocaine being used in this investigation.

2 STUDY OBJECTIVES AND ENDPOINTS

2.1 Objectives

2.1.1 Effectiveness

The primary objective of the study is to demonstrate the effectiveness of Radiesse (+) following deep (subdermal and/or supraperiosteal) injection to improve the contour of jawline by adding volume to the jawline.

2.1.2 Safety

The safety objectives include the identification and description of adverse events (AEs) and serious adverse events (SAEs) during the course of the study.

2.2 Endpoints

2.2.1 Primary endpoint

Comparison of the responder rate between the treatment group and the untreated control group at Week 12, according to the Merz Jawline Assessment Scale (MJAS). Treatment response is defined as ≥ 1 -point improvement.

2.2.2 Secondary endpoints

[figure not shown]
- FACE-Q satisfaction of the lower face and jawline for treated subjects as average percent change from baseline to Week 12.
- Global Aesthetic Improvement Scale (GAIS) scores for treated subjects at Week 12, as completed by the treating investigator.
- GAIS scores for treated subjects at Week 12, as completed by the subject.

[figure not shown]
[REDACTED] responder rates in the treatment group and the untreated control group at Week 12, according to the MJA [REDACTED]

[figure not shown]
[REDACTED] Treatment response is defined as ≥ 1 -point improvement [REDACTED]

[figure not shown]
[REDACTED].

2.2.3 [REDACTED]

2.2.4 *Safety endpoints*

2.2.4.1 *Primary safety endpoints*

- Incidence and nature of device- and/or injection-related AEs and SAEs observed during the study.

2.2.4.2

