3.2.1.1 Merz Jawline Assessment Scale (MJAS)

As individuals age, the loss of volume and the descent of the jowl and facial soft tissue creates a defined, contour irregularity with formation of a post-jowl and possibly a pre-jowl defect. The MJAS [REDACTED] was developed to grade the loss of volume and disruption of contour in the jawline region. The 5-point MJAS illustrates the progression of severity.

[REDACTED]

[figure not shown]

[figure not shown]

3.2.1.3 *Treating Investigator Global Aesthetic Improvement Scale (GAIS)*

The treating investigator will use the GAIS to assess global aesthetic improvement among treated subjects [REDACTED].

[figure not shown]

[figure not shown]
Refer to the study endpoints (see [Section 2.2](#)) and visit schedules (see [Sections 5.1.1](#) and [5.1.2](#) [REDACTED]) for additional information regarding the GAIS assessments and the associated reference time points.

3.2.1.4 *Subject Global Aesthetic Improvement Scale (GAIS)*

Treated subjects will evaluate their overall aesthetic improvement on the subject GAIS

[figure not shown]

[figure not shown]
3.2.1.5 *FACE-Q Instruments* [REDACTED]

Treated subjects will evaluate the treatment outcome using [REDACTED] FACE-Q instruments.

[figure not shown]
[REDACTED] With respect to the jawline treatment within this

study, [REDACTED] FACE-Q assessments will be completed by all subjects at baseline and at multiple study visits [REDACTED]
[REDACTED]

3.2.2

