
Visit 2 (Week 2 post-treatment): Day 14 (\pm 3 days)

- Review and record changes in any concomitant medications/procedures. Confirm subject remains compliant with any applicable study restrictions.
- Review and record any AEs.

[figure not shown]
Visit 3 (Week 4 post-treatment): Day 29 (+ 3 days)

[figure not shown]
- Review and record changes in any concomitant medications/procedures. Confirm subject remains compliant with any applicable study restrictions.
- Review and record any AEs.

- [REDACTED] MJAS assessment.

[figure not shown]
- Have subject complete the Subject GAIS.

- Administer FACE-Q assessments to subject.

- Administer Treating Investigator GAIS.

Injection (only for subjects who receive a touch-up treatment):

- Perform urine pregnancy test (if female of childbearing potential).
- Administer touch-up injection as follows:
 - If a subject does not achieve a \geq 1-point improvement [REDACTED]

[REDACTED], a touch-up will be required to achieve optimal correction.

- If a subject achieves a \geq 1-point improvement on the MJAS [REDACTED] a touch-up may be done [REDACTED]

Visit 4 (Week 6 post-treatment): Day 42 (\pm 3 days)

Note: This visit is only for subjects who received a touch-up at Week 4.

- Review and record changes in any concomitant medications/procedures. Confirm subject remains compliant with any applicable study restrictions.
- Review and record any AEs.

Visit 5 (Week 12 post-treatment): Day 84 (\pm 3 days)

- Review and record changes in concomitant medications/procedures. Confirm subject remains compliant with any applicable study restrictions.
- Review and record any AEs.

- Record height and weight for BMI.
- [REDACTED] MJAS assessment.

- Have subject complete the Subject GAIS.

- Administer FACE-Q assessments to subject.

- Administer Treating Investigator GAIS.

Visit 6 (Week 24 post-treatment): Day 168 (\pm 10 days)

- Review and record changes in concomitant medications/procedures. Confirm subject remains compliant with any applicable study restrictions.
- Review and record any AEs.
- [REDACTED] MJAS assessment.

- Administer FACE-Q assessments to subject.

- Administer Treating Investigator GAIS.

Visit 7 (Week 36 post-treatment): Day 252 (\pm 10 days)

- Review and record changes in concomitant medications/procedures. Confirm subject remains compliant with any applicable study restrictions.
- Review and record any AEs.
- [REDACTED] MJAS assessment.

- Have subject complete the Subject GAIS.

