6.3 Study treatment

All protocol-specific criteria for the administration of study treatment must be met and documented prior to administration of any study treatment. All device administration (injection) will be performed on site by the treating investigator. Subjects will not be dispensed any investigational material. Any noncompliant subject or site may be discontinued from the study (see [Section 5.2](#)).

6.3.1 *Planned treatment procedure and administration*

Approximately 120 subjects will be randomized to receive Radiesse (+) and 60 subjects will serve as the controls/delayed treatment. Subjects will be randomized using a 2:1 allocation ratio for treatment to control.

Subjects randomized to treatment at baseline will receive an initial Radiesse (+) injection in both jawlines.

Subjects who do not achieve a \geq 1-point improvement on the MJAS [REDACTED] will be required to have a touch-up injection [REDACTED]. [REDACTED] the treating investigator will be responsible for establishing whether the \geq 1-point MJAS improvement threshold is met [REDACTED]

In addition, subjects who achieve a \geq 1-point improvement on the MJAS [REDACTED] may have a touch-up [REDACTED] at the discretion of the treating investigator and the subject. These subjects are also eligible for retreatment at Week 48 if the subject and investigator are in agreement that retreatment is needed. [REDACTED]

After completion of all study assessments associated with the primary endpoint at Week 12, subjects randomized to the control group will be treated with Radiesse (+) (i.e., delayed treatment).

Subjects who did not achieve a \geq 1-point improvement on the MJAS [REDACTED] will be required to have a touch-up injection [REDACTED]. [REDACTED]

the treating investigator will be responsible for establishing whether the \geq 1-point MJAS improvement threshold is met [REDACTED]

In addition, subjects who achieve a \geq 1-point improvement on the MJAS [REDACTED] may have a touch-up [REDACTED] at the discretion of the treating investigator and the subject. [REDACTED]

6.3.1.1 *Jawline region and treatment area*

[figure not shown]
All study injections will be performed by the site's principal investigator (PI). The PI is also described as the treating investigator in this document.

Observed adverse events will also be recorded.

The jaw region is defined as follows:

- Anterior to posterior boundaries: from the anterior aspect of the pre-jowl sulcus to just anterior to the earlobe.

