8.2 Randomization

The randomization procedure that will be implemented for this study will be a block-stratified technique [REDACTED]

[REDACTED]. The randomization will be computer generated by a statistician independent of the study team. Block stratification will ensure there is an adequate statistical power for demonstrating the effectiveness [REDACTED]

[REDACTED]. Accordingly, approximately 120 subjects will be randomized to treatment and 60 subjects to control. [REDACTED]

[REDACTED] All subjects in the control/delayed-treatment group (60 subjects) will receive treatment at their Week 12 [REDACTED]

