6 ENDPOINTS FOR ANALYSIS

6.1 Effectiveness Endpoints

6.1.1 *Primary effectiveness endpoint*

[figure not shown]
Comparison of the responder rate between the treatment group and the untreated control group at Week 12, according to the Merz Jawline Assessment Scale (MJAS) [REDACTED]. Treatment response is defined as ≥ 1 -point improvement [REDACTED]. The study device will be clinically effective if at least 50% of treated subjects are responders.

[figure not shown]
6.1.2 *Secondary effectiveness endpoints*

[figure not shown]
- [REDACTED] FACE-Q satisfaction of the lower face and jawline for treated subjects [REDACTED] as average percent change from baseline to Week 12. [REDACTED]
- [REDACTED] Global Aesthetic Improvement Scale (GAIS) scores for treated subjects at Week 12, as completed by the treating investigator. [REDACTED]
[REDACTED]
- [REDACTED] GAIS scores for treated subjects at Week 12, as completed by the subject. [REDACTED]
- [REDACTED] responder rates in the treatment group and the untreated control group at Week 12, according to the MJAS [REDACTED]
[REDACTED]
[REDACTED]
Treatment response is defined as ≥ 1 -point improvement [REDACTED]
[REDACTED]
[REDACTED].

6.1.3 [REDACTED]

[REDACTED]

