7 STATISTICAL ANALYSIS METHODS

7.1 Effectiveness Endpoints

The primary effectiveness analysis and the analysis of the secondary effectiveness endpoints will be based primarily on the ITT and additionally, for sensitivity purposes, on the PP. [REDACTED]

[REDACTED] Statistical tests on the primary effectiveness endpoint will be conducted as a one-sided hypothesis to determine evidence of between-treatment differences.

For summary purposes, continuous variables (values and changes from baseline) will be summarized by n, mean, standard deviation (SD), median, minimum, and maximum. For qualitative variables, absolute and percent frequencies (n, %) and, if applicable, shift tables will be displayed. For all test statistics used for analyzing the effectiveness endpoints, p-values will be used either for inferential or for descriptive purposes, as appropriate.

Change from baseline is defined as post-baseline value minus the corresponding baseline value; percent change from baseline is defined as change from baseline divided by the corresponding baseline value, expressed in percentage.

P-values will be reported to four decimal places (e.g. p=0.0375). P-values below 0.0001 will be presented as '<0.0001'.

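### As visibly defined, the FACE-Q secondary endpoint is an uncontrolled average of individual percent changes, although controls are scheduled to complete FACE-Q at baseline and at Week 12

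*Protocol*

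**What the plan says.** - **Definition.** Protocol 2.2.2 gives the endpoint as "FACE-Q satisfaction of the lower face and jawline for treated subjects as average percent change from baseline to Week 12". The protocol synopsis has the same content: "FACE-Q satisfaction with lower face and jawline among treated subjects as average percent change from baseline to Week 12". SAP 6.1.2 opens its bullet with "FACE-Q satisfaction of the lower face and jawline for treated subjects" and, after a redaction, also specifies average percent change to Week 12.
- **Metric.** SAP 7.1 states that "percent change from baseline is defined as change from baseline divided by the corresponding baseline value, expressed in percentage". The same section also plans n, mean, SD, median and range for values and absolute changes of continuous variables.
- **Analysis.** Protocol 8.4.1.2 and SAP 7.1.2 describe descriptive summaries of sum and Rasch-transformed scores among treated subjects; the rest of each bullet is redacted. SAP 7.1.2 uses ITT with observed cases. The MJAS responder secondary endpoint in the same lists is summarised in both arms.
- **Who completes FACE-Q.** Protocol 3.2.1.5 says "FACE-Q assessments will be completed by all subjects at baseline and at multiple study visits". In Protocol 5.1.1 and 5.1.2 the instruction "Administer FACE-Q assessments to subject" appears for the treatment group at baseline and Week 12. For controls it appears at Visit 1 and at Visit 3 (Week 12), where it is listed above the delayed injection.

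**The concern.** Two features of the visible definition weaken the estimate.

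First, it has no comparator. A change from baseline in self-reported satisfaction among treated subjects mixes the treatment effect with time trend, regression to the mean and the effect of repeating a questionnaire. A randomised untreated arm removes these, and here that arm appears to supply the scores needed.

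Second, the metric is an average of individual ratios. Subjects with low baselines weigh heavily, and ordinary fluctuation raises the average even when the mean score does not move.

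At stake is a supportive figure in a pivotal pre-market study. It could be read as a treatment effect when part of it is not.

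**Working it through.** The documents state no FACE-Q effect size, SD, range, repeatability or power, so there is no planned figure to reproduce.

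**1. Is a control comparison available?** Protocol 3.2.1.5 covers all subjects at baseline. Protocol 5.1.2 lists FACE-Q at control Visit 3 (Week 12) before the injection heading. Protocol 6.3.1 adds "After completion of all study assessments associated with the primary endpoint at Week 12, subjects randomized to the control group will be treated", but that sentence covers only assessments tied to the primary endpoint, which is MJAS. That FACE-Q precedes the control injection therefore rests on list order. The instrument names are redacted, so it is inferred that the controls' set includes the lower face and jawline scale.

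**2. Upward bias of averaged percentages (illustration).** Let half the subjects have baseline a and half r·a, and let a fraction s of each half switch to the other value. Mean absolute change is 0. The baseline-to-Week-12 correlation is rho = 1 - 2s, so s = (1 - rho)/2. Switchers contribute r - 1 or 1/r - 1, so

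mean percent change = [(1 - rho)/2] × (r + 1/r - 2)/2.

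With rho assumed to be 0.3 to 0.7, the first factor runs from 0.35 down to 0.15.

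| r | (r + 1/r - 2)/2 | × 0.15 (rho 0.7) | × 0.35 (rho 0.3) |
|---|---|---|---|
| 1.25 | 2.5% | 0.4% | 0.9% |
| 1.5 | 8.3% | 1.3% | 2.9% |
| 2 | 25% | 3.8% | 8.8% |

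A simulation with no true change and scores bounded at 5 and 100 gives the same direction. All its inputs are assumed. Mean individual percent change was +5.2%, +7.7% and +10.3% for baseline mean 40, SD 15 and correlation 0.8, 0.7 and 0.6. At correlation 0.7 it was +8.4% for mean 30, SD 12 and +4.1% for mean 50, SD 15. Mean absolute change was about 0 throughout.

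**3. Precision of the randomised difference.** Inputs: 120 and 60 subjects (Protocol 4.1). Results are in units of the SD of change, which is not given.

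- SE = sqrt(1/120 + 1/60) = sqrt(0.025) = 0.158.
- Unadjusted 95% half-width = 1.96 × 0.158 = 0.31 SD.
- With an assumed 10% missing (108 against 54): 1.96 × 0.1667 = 0.33 SD. With an assumed 20% missing (96 against 48): 1.96 × 0.1768 = 0.35 SD.
- Baseline adjustment, with equal variances assumed, multiplies the SE by sqrt((1 + rho)/2). This is 0.806 at rho 0.3 and 0.922 at rho 0.7, giving half-widths of 0.25 and 0.29 SD.

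**The case against.** The strongest objection is redaction. Text is blacked out inside and after the FACE-Q bullet in SAP 6.1.2, and directly after the descriptive-statistics wording in Protocol 8.4.1.2 and SAP 7.1.2. Protocol 2.2.3 and 8.4.1.3 and SAP 6.1.3 and 7.1.3 are hidden altogether. A reader might infer that no control comparison of FACE-Q is planned, or that the control data are discarded. The documents do not support either reading. The hidden text may contain the comparison. The term treated subjects also does not visibly exclude controls after their delayed treatment; their Week 12 visit is itself labelled Day 1/Baseline in Protocol 5.1.2. This limits the point to the visible definition but does not remove it.

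A reader might also take the middle column of the table (2.5%, 8.3%, 25%) as the likely inflation. Those values need every low scorer to become a high scorer and the reverse, which is a correlation of -1. The two right-hand columns are the usable illustration.

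Three further objections stand in part. SAP 7.1 already summarises absolute change, so what is not visible is the between-arm contrast and its place as the endpoint. FACE-Q sits beside two treated-only GAIS endpoints as descriptive data, with no visible test, alpha or success threshold. Subjects know whether they were injected, so a between-arm difference in self-report still carries expectation effects; it does remove time trend and regression to the mean.

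**Conclusion.** The point holds in limited form. As visibly defined, the endpoint is an uncontrolled average of individual percent changes, and such an average is biased upward by score fluctuation. The direction is certain, but the size cannot be fixed from the documents. In the two-value illustration it runs from about 0.4% to 8.8% across factors of 1.25 to 2 and an assumed correlation of 0.3 to 0.7.

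The conclusion rests on three readings: that average percent change means the mean of individual ratios under the SAP 7.1 formula, that controls complete this scale, and that they do so before injection, as the list order indicates.

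Severity is minor. The primary MJAS hypotheses, their tests and their alpha are unaffected, so nothing here bears on whether the trial meets its primary objective.

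**What to change.** Unless redacted text already does this, define the endpoint analysis as the treatment minus untreated-control difference in absolute FACE-Q change from baseline to Week 12. Use ITT with observed cases, as SAP 7.1.2 already plans. Give a 95% confidence interval from a model adjusted for baseline score and the randomisation strata. Protocol 8.2 states "The randomization procedure that will be implemented for this study will be a block-stratified technique", although the strata themselves are redacted. Keep percent change as a descriptive summary, and state whether it uses the sum or the Rasch-transformed score if hidden text does not. Note in the report that subjects knew their assignment.

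If hidden text already contains this comparison, make it the stated analysis of this endpoint. If controls do not complete this scale, make absolute change, already summarised under SAP 7.1, the endpoint metric.

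The cost is endpoint and SAP wording plus one model, with no new visits or subjects if controls complete the scale. The downsides are a headline that may look less favourable than a treated-only percentage, and expectation effects that the comparison cannot remove.
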